9.4 STATISTICAL ANALYSES

9.4.1 GENERAL APPROACH

Outcome data is derived from the administrative claims and worker surveys.

Administrative claims will be collected over two periods (06/01/2019-05/31/22) and (06/01/2022-05/31/2023). All three outcomes of interest are primary outcomes. The analysis will examine the group level change of the outcome, adjusting for length of time in each period, to show a reduction in impaired health or behaviors that may be due to implementation of the intervention.

Worker surveys will be collected by member worker surveys from each health fund at two points in time. The baseline, before implementation of the intervention, and at 6-months after start of implementation. All members will be invited to complete a survey. The desired sample is 300 surveys per health fund at each time point. The outcomes are composed of one or more items in the surveys. Group level statistics will be computed as the proportion of members with a positive response to each outcome. The change in proportion by time point may be due to implementation of the intervention.

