9.4.2 ANALYSIS OF THE PRIMARY ENDPOINT(S)

- a) Administrative Claims
 - a. Outcome variables of interest
 - i. Opioid misuse- “Overlapping Rx” OR “Multiple Rx on same day, different provider”
 - ii. Chronic opioid use- more than 60 days supply in a 90 day window
 - iii. Opioid use disorder- ICD-10 T40* (Poisoning by, adverse effect of and underdosing of narcotics and psychodysleptics) &/Or ICD-10 F11* (opioid related disorders) &/or prescribed MAT (Drug name contained “methadone” or “buprenorphine”; picks up buprenorphine, suboxone, zubsolv, naltrexone, methadone, narcan, and vivitrol)
 - b. Compute statistics for baseline period (06/01/2019-05/31/2022) and follow-up (06/01/2022-05/31-2023)

- i. Categorical data will be presented as N (%), continuous data as median (25th, 75th %tile)
- c. Run comparisons between baseline and follow-up time points
 - i. Comparisons involving two categorical variables will be made using Fisher's exact test
 - ii. Comparisons involving a continuous variable and a categorical variable will be made using Wilcoxon Rank Sum test or Kruskal Wallis test

b) Worker Survey

- a. Outcome variable of interest
 - i. Opioid misuse- Participant responded yes to one of the following two questions:
 - 1. Did you use the pain medication more than prescribed, or for a longer period than prescribed? [pnmed_longer]x
 - 2. Have you used prescription pain medications that were prescribed to someone else? [pnmed_othersrx]x
 - b. Compute the change at 6 months post-intervention (change of opioid misusep) of group-level data collected from groups of health

All endpoints are independent outcomes.

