9.4.8 TABULATION OF INDIVIDUAL PARTICIPANT DATA

Administrative claims data will be combined using a unique linking variable. The claims data will include the date of service in order to identify the time point. Three years of data will be collected at baseline (May 2019-May 2022) and one year of data for follow up (June 2022-May 2023). The data will be analyzed as group level data by time point.

The worker surveys will be analyzed as group level data by time point. The data will not be tabulated by individual participants, nor will the administrative data be linked to the worker survey data.

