93. *The Family and Medical Leave Act of 1993: Leave for Treatment of Substance Abuse*. 1993 [cited 2021 September 23]; Available from: <https://www.law.cornell.edu/cfr/text/29/825.119>.

94. Substance Abuse and Mental Health Services Administration. *Plan and Implement a Program*. 2020 [cited 2021 October 14]; Available from: <https://www.samhsa.gov/workplace/toolkit/plan-implement-program>.

95. Substance Abuse and Mental Health Services Administration. *Tip 63: Medications for Opioid Use Disorder*. 2018 2021 [cited 2021 October 13]; Available from: https://store.samhsa.gov/sites/default/files/SAMHSA_Digital_Download/PEP21-02-01-002.pdf.

96. Howard, J., et al., *Medication-Assisted Treatment for Opioid Use Disorder*. Workplace Solutions, 2019.

E. Monthly Health Fund meeting script_followup

Monthly Health Fund follow-up meeting:

Date: _____

Organization: _____

Participant: _____

Notes from past Interview:	
1. Are you in the process of making any changes to your opioid prevention program? If yes please describe (date of adoption,	

implementations strategies, how are you measuring effectiveness of the change, participation rates in programs for workers, adherence to and enforcement of policies, and methods for disseminating programs)
 
a. Have you made any changes to existing opioid prevention programming? If so please explain
	

2. Did you review the guidelines? If yes, what did you find useful and what do you think is missing from the guidelines?
 
a. Did you complete the needs assessment?b. Did you follow the process guide, steps 1, 2, and 3?c. What did you list on your inventory of resources?d. Did you make a plan?	

3. What are challenges or barriers are you encountering in trying to implement your program?
	

G. Data management of Administrative Health Claims and Worker Surveys
Data management of Administrative Health Claims and Worker Surveys

a) Administrative Health Claims

a. Inclusion

- i. Health plan member (as opposed to dependent or retired) at some point during study period (6/1/2019-5/31/2022), per census records
 - 1. Could transition to retired status during study period, but needed to start as member

b. Exclusion

- i. Missing eligibility or termination dates in census records
- ii. Cancer diagnosis
 - 1. Ever received ICD-10 code in medical claims data: C00.x–C26.x, C30.x–C34.x, C37.x–C41.x, C43.x, C45.x–C58.x, C60.x–C76.x, C77.x–C85.x, C88.x, C90.x–C97.x)

c. Initial work

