 - 1. Serial prescriptions (most common scenario)
 - a. Start with all opioid first fills (including unlinked and linked with medical claims, using the process above)

- b. Arrange all fills by UID and fill date
 - c. Assign fills to claims that 1) occur after a claim with a linked opioid fill, and 2) opioid fill date is no more than 30 days after previous fill runout date (fill date + days supply)
2. Refills specified in the pharmacy data
 - a. Join opioid refills (from 1b above) with the first fills using prescription identifier ("RXNUM").
 - b. Assign claim information from first fills to linked refills

Variable definitions

- e. Opioid-related variables. These variables were generated using information from the medical claims and pharmacy fill data from the health fund and the CDC opioid file "CDC opioid NDC_oral MME conversion_update_2020.xlsx". The CDC file was merged with health fund pharmacy fill data on NDC
 - i. Medication assisted treatment (MAT): Drug name contained "methadone" or "buprenorphine" in either file or drug description was "ANTIDOTES AND SPECIFIC ANTAGONISTS" in the pharmacy fill file
 1. This strategy picks up buprenorphine, suboxone, zubsolv, naltrexone, methadone, narcan, and vivitrol
 - ii. Opioid: pharmacy class was "opioid" in the CDC file, and the drug was not already identified as MAT (see above)
 - iii. OUD: ever ICD-10 code "T40x" or "F11x" on a medical claim or identified as MAT (see above)
 - iv. Days supply > 7 days: based on "days supply" as provided in fill data
 - v. MME/day: Instructions for calculation are in CDC file. Formula is "strength per unit" * "average quantity per day" * "MME conversion factor"
 - vi. Overlapping Rx: Date opioid fill is within previous days supply (current fill date < previous fill date + days supply)
 1. When the previous prescription is a "short course" (the prescription window is encompassed by prescription before it), the prescription before the short course is used in evaluation
 - vii. Chronic use (>60 days supply in a 90 day window)
 1. For each worker time is divided into 90 day "cycles", starting with the date of the first opioid fill
 2. Days supply is totaled within the 90 day cycle
 3. If the individual had opioid fills later than 90 days after the first fill, a new cycle is started and the process starts over
 4. When workers have multiple opioids filled on the same day, use the longest days supply in calculations

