 5. Indicator variable for total days supply in a cycle > 60 for any given cycle
 - viii. Multiple Rx in a single visit: multiple Rx filled on the same day and NPI is the same between fills

- ix. Multiple Rx on same day, different provider: multiple Rx filled on the same day and NPI between Rx different. Could indicate doctor shopping
- x. Misuse: “Overlapping Rx” OR “Multiple Rx on same day, different provider”
- f. Diagnoses. These variables were generated from information in the medical (i.e diagnosis and procedure) claims. Diagnoses are assessed at the claim level, and “rolled up” to the worker (i.e, has worker ever had a diagnosis for X)
 - i. MSD surgery: CPT codes 20005-21010; 21500-22900; 62263-63746; 64400-64999
 - ii. Acute MSD injury: ICD-10 codes ranging S00-T14
 - iii. Chronic MSD: ICD-10 codes M.x, G54-G57
 - iv. Recurring acute injury. Acute MSD injuries that occur across multiple claims are recoded as “recurring injuries”. These are combined with chronic MSD for our purposes
 - 1. ICD-10 codes for acute MSD injuries are identified on a given claim (see above)
 - 2. If the same ICD-10 code occurred on a previous claim more than 30 days before the claim in question, the acute MSD injury is recoded as “recurring injury” on the claim in question and will no longer be counted as an acute MSD injury
 - 3. Using this method, the first occurrence of a given acute MSD injury ICD10 code will be left as “acute MSD injury”
 - v. Other diagnosis: Claims that do not fit into i-iv above are coded as “other Dx”
 - vi. Acuity: claims can have multiple diagnoses associated with them. Acuity is assigned as follows, regardless of other diagnoses associated with the claim: MSD surgery, Acute MSD Injury, recurring injury or chronic MSD, other diagnoses.
 - 1. So if a claim had codes for both MSD surgery and chronic MSD, the acuity is assigned to MSD surgery
- g. Description of the study sample [all data are in “claims eligibility_20230213.docx”, unless otherwise noted]
 - i. Demographics and worker characteristics
 - 1. Gender
 - 2. Age in 2022
 - 3. Plan status (Active, COBRA, etc)
 - 4. Time worker eligible for benefits during study period
 - 5. Gaps in eligibility
 - ii. Plan utilization
 - 1. Proportion of workers with a health claim, pharmacy claim, overlap of these
 - iii. Distribution of diagnoses based on original order of acuity
 - iv. Diagnoses. Number of workers with:
 - 1. MSD surgery
 - 2. Acute MSD injury

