3. Chronic MSD or recurring acute injuries
4. Other diagnoses

- v. Opioid utilization. Number of workers with:
 1. At least one opioid fill
 2. Ever days supply > 7
 3. Ever MME/day > 50
 4. Ever MME/day > 90
 5. Overlapping Rx
 6. Chronic use (>60 day supply in 90-day period)
 7. Multiple Rx on the same day, same provider
 8. Multiple Rx on the same day, different providers
 9. Misuse
- vi. OUD
 1. N by source (diagnosis, MAT fill, both)

- h. Medical claim/opioid linked data
 - i. Distribution of opioid fills by diagnosis, as captured on linked claim

- b) Worker Surveys
 - a. Worker surveys will be distributed to all members of each health fund at start of project, to collect a sample of 300 surveys. We will collect another sample of 300 surveys after 6 months.
 - b. We will examine the serial cross sectional data (baseline & 6mos) by comparing sample characteristics.
 - Age, x
 - gender, x
 - race, x
 - hisp, x
 - unionbenefits, x
 - employstatus, x
 - time_construction, x
 - months_construction, x
 - constype;x
 - c. We will examine the items related to each of the three outcomes of interest
 - i. Opioid misuse- A “yes” response to either of the following two items:
 1. Did you use the pain medication more than prescribed, or for a longer period than prescribed? [pnmed_longer]x
 2. Have you used prescription pain medications that were prescribed to someone else? [pnmed_othersrx]x
 - ii. Proportion of workers with lost time- A “yes” response to either of the following two items:

1. Please refer to the last 12 months for the following questions: Did you miss any days of work because of your pain or discomfort? [missday_pn]x
2. In the past 12 months, have you gone to work intoxicated, high, or recovering from the night before? [missday_intox] [*possible reduced productivity]x
- iii. Proportion of workers who are willing to seek help
 - 1) their workplace
 1. If I was struggling with a substance use problem... I would be willing to seek help from my supervisor or someone in human resources [help_sup_hr]x
 2. If I was struggling with a substance use problem... I would be willing to seek help from a professional (MAP or behavioral health) [help_prof]x
 3. If I was struggling with a substance use problem... I would be willing to ask a trusted coworker for help [help_coworker]x
 4. Have you attended Alcoholics or narcotics anonymous (AA/NA) group [aa_na_use]x
 5. Have you met with the specialist? [peer_supp_use]x

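### Section 9.4.1 promises to adjust the claims outcomes for period length, but the comparison in 9.4.2 (N (%) over 36 and 12 months, Fisher's exact test) has no means of doing so

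*Combined protocol and SAP*

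**What the plan says.** Section 9.4.1 on the claims outcomes: "The analysis will examine the group level change of the outcome, adjusting for length of time in each period". It adds that the purpose is to show a reduction that may be due to the intervention. It names no method of adjustment.

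Section 9.4.2 gives the computation: "Compute statistics for baseline period (06/01/2019-05/31/2022) and follow-up (06/01/2022-05/31-2023". Categorical outcomes are summarised as N (%), and "Comparisons involving two categorical variables will be made using Fisher's exact test". Continuous data get a Wilcoxon rank sum or Kruskal-Wallis test.

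The data-management appendix defines the outcomes per worker:
- Opioid use disorder: "OUD: ever ICD-10 code" (T40x or F11x), or a medication-assisted-treatment fill.
- Chronic use: "Indicator variable for total days supply in a cycle > 60 for any given cycle".
- Misuse is reported in a list headed "Opioid utilization. Number of workers with".

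The appendix includes anyone who was a plan member "at some point during study period (6/1/2019-5/31/2022), per census records", so its study period ends before follow-up starts. Section 9.4.8 says of the two periods: "The claims data will include the date of service in order to identify the time point".

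**The concern.** An ever/any indicator accumulates with observation time: three years give a worker three times as long as one year to acquire a qualifying diagnosis, a chronic-use cycle or an overlapping fill. Setting a three-year proportion against a one-year proportion therefore builds in a difference that has nothing to do with the guidelines. The authors evidently saw this, because 9.4.1 promises an adjustment, but the procedure in 9.4.2 does not contain it.

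This is a primary endpoint whose change is to be read as a possible intervention effect. Sections 9.1 and 9.2 also send the data into the power calculation for a future trial, so a distorted baseline and change would carry over into that design.

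**Working it through.** **Is there an adjustment anywhere?**
- 9.4.2: N (%), Fisher, Wilcoxon and Kruskal-Wallis have no exposure term.
- 9.3: members are censored when they lose eligibility, but no estimator uses the censored time.
- 9.4.8: group-level analysis by time point only.
- Appendix: eligible time and eligibility gaps are listed only to describe the sample.

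There is no rate, offset, annualisation or matched window.

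**Figures from the documents.** Baseline 06/01/2019-05/31/2022 = 1,096 days; follow-up 06/01/2022-05/31/2023 = 365 days; 1,096/365 = 3.0. Section 9.2 expects 10,200 members per fund, and 3 × 10,200 = 30,600, as stated there.

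**Assumptions, because the documents give no prevalence, recurrence or turnover.** Constant annual prevalence p of 1%, 2% or 5%; no true change; flags reset in each window; a share r of each year's cases recurs every year. Resetting is inferred from 9.4.8 (date of service) and from the appendix definitions being written for a period ending 5/31/2022.

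**Full eligibility.** With q = (p − rp)/(1 − rp), the proportion flagged in T years is

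p_T = rp + (1 − rp)[1 − (1 − q)^T], and the false reduction is 1 − p_1/p_3.

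Example, p = 0.02 and r = 0.5: q = 0.01/0.99 = 0.0101; p_3 = 0.01 + 0.99 × 0.0300 = 0.0397; p_1 = 0.02; false reduction = 1 − 0.02/0.0397 = 49.6%.

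**Turnover.** Open cohort of constant size with exit rate L per year in both windows; mean eligible time = T/(1 + LT). L = 1/6 gives 2.0 baseline years and 0.86 follow-up years; L = 1/3 gives 1.5 and 0.75. With h = −ln(1 − q), k = L + h, F = (h/k)(1 − e^(−kT)) and I = (h/k)[T − (1 − e^(−kT))/k]:

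p_T = rp + (1 − rp)(F + L·I)/(1 + LT).

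| False reduction, p = 1-5% | r = 0 | 0.5 | 0.8 | 0.9 | 1 |
|---|---|---|---|---|---|
| Full eligibility | 65-66% | 49-50% | 28% | 17% | 0% |
| Mean 2.0 and 0.86 years | 55-57% | 37-38% | 19% | 10% | 0% |
| Mean 1.5 and 0.75 years | 48-50% | 29-30% | 14% | 7% | 0% |

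In counts, one fund of 10,200 at p = 2% with full eligibility has 600, 405, 285 or 245 flagged workers at baseline (r = 0, 0.5, 0.8, 0.9) against 204 in follow-up.

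**If the opioid use disorder flag is carried forward** (four-year against three-year ever, same members), the false ratio p_4/p_3 is 1.30-1.33, 1.24-1.25, 1.14, 1.08 and 1.0 for the same r: a false increase.

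**Does a simple shortcut work?** Dividing the three-year proportion by three gives a false ratio p_1/(p_3/3) of 1.01-1.05, 1.5, 2.1, 2.5 and 3.0. A 36-month member-month rate that counts each worker once goes wrong in the same direction. Either is close to right only when cases do not recur.

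**The case against.** The strongest reply is that 9.4.1 is part of the plan too. Read with 9.4.2, it leaves a method unspecified rather than contradicting it, and Fisher's test would serve once outcomes were put on equal windows. That is fair as far as it goes: the false changes above arise only if 9.4.2 is run as written. But 9.4.2 names its two windows explicitly and they are not equal, so following it means dropping the promise in 9.4.1. The sponsor has not proposed dividing by three; it is tested because it is an obvious way to honour 9.4.1, and it fails whenever cases recur.

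Second, size and direction rest on assumptions. This stands for size: the documents supply only the 3-to-1 ratio, and faster turnover shrinks the effect (at an exit rate of 1 per year, 33%, 14% and 5% for r = 0, 0.5 and 0.8 at p = 1%). The turnover model also counts recurring cases in full whatever their eligible time, so its 0% at r = 1 is built in. Direction is settled only if flags are reset.

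Third, this is a single-arm study that disclaims formal hypothesis testing (9.1) and defines success as recruiting funds and collecting measures (section 3). That limits the consequence and is why the point is not rated higher.

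**Conclusion.** The concern holds. Sections 9.4.1 and 9.4.2 are not reconciled, and the computation in 9.4.2 yields a distorted change when nothing has changed. With flags reset in each window the error is a false reduction, from 0% (every case recurs every year) to about 66% (no recurrence, full eligibility), under assumed prevalences of 1-5%. High recurrence is plausible for opioid use disorder and chronic use, so the size may differ between outcomes. With the opioid use disorder flag carried forward, that outcome errs the other way, by a ratio of up to 1.33.

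With flags reset, the window mismatch does not affect the 12-month follow-up proportion; the baseline figure and the change are affected. The harm is a misleading description and planning input, not a false trial conclusion. It should be fixed.

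**What to change.** In 9.4.1 and 9.4.2:

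1. Derive each claims outcome in equal 12-month windows by date of service, with flags reset in each window. State how a 90-day cycle or overlapping fill that crosses a boundary is assigned.
2. Compare 06/2021-05/2022 with 06/2022-05/2023 and show the two earlier years descriptively. Equal length is the essential point; the mean of the three annual baseline proportions is an acceptable alternative.
3. Take each denominator from members eligible in that window under the 9.3 censoring rule, or use cases per eligible member-month within that window.
4. Replace the unpaired Fisher p-value with a difference or ratio and a 95% CI that allows for members present in both windows.

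The same comparison needs three related items settled. The population ends in May 2022 in 9.3 and the appendix but in May 2023 in sections 5 and 5.1. Follow-up is 6 months in 9.1 but 12 months in 9.4. Each fund's intervention start date should be stated: the guideline file carries the date 07062022, and if that means 6 July 2022, at least 35 of the 365 follow-up days (9.6%) precede that version. A file name is only indirect evidence of a start date.

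**Cost.** SAP wording and re-derivation of flags from dates the claims already carry. Eligibility and termination dates are needed for the follow-up year. The requested-variables list shows none, although the appendix uses census records for baseline, so an added data request may be needed. There will be fewer baseline cases (204 per fund instead of 245-600 in the 2% example) and probably a less favourable apparent change. Precision, as an unpaired 95% half-width 1.96·√(2p(1 − p)/n) at p = 1%, 2% and 5%, is 0.27, 0.38 and 0.60 percentage points for n = 10,200, and 0.16, 0.22 and 0.35 for n = 30,600, ignoring clustering by fund.

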9 STATISTICAL CONSIDERATIONS

9.1 STATISTICAL HYPOTHESES

This is a feasibility trial to evaluate the ability to recruit and enroll health funds, collect endpoint data for primary and secondary outcome measures, and to collect process measures related to implementation of the intervention with three health funds. There is no formal hypothesis testing in this trial although we will calculate descriptive statistics at baseline and follow-up (6-months) to show change over time. The data will be used to compute statistical power for a future R01 if the current study is successful.

- Primary Endpoint(s):
 - a) We will calculate the Proportion of workers with opioid misuse, opioid use disorder and opioid overdose using administrative data. We will assess change of opioid misuse and opioid use disorder at 6 months following delivery of the intervention
 - b) We will calculate the proportion of workers with opioid misuse from worker surveys. We will assess change in opioid misuse at 6 months following delivery of the intervention.

- Secondary Endpoint(s):
 - a) We will calculate the proportion of workers with lost time using worker surveys. We will assess change in reported lost time at 6 months following delivery of the intervention.
 - b) We will calculate the proportion of workers reporting willingness to seek help for opioid abuse using worker surveys. We will assess change in reported willingness to seek help at 6 months following delivery of the intervention.

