- i. Medical claims (“claims”), pharmacy claims (“fills”), census data was received “piecemeal”
 - 1. By timeframe (i.e, quarterly) and type (plan member, dependent, retired)

- ii. Consolidate files into single datasets for claims, fills, census data and work histories
- iii. Create eligible/valids file—this is the list of members eligible for the study, based on above criteria
- iv. Limit all analysis data (claims, fills) to members in the eligible/valids list
- d. Opioid/claim linkage: The process of linking opioid prescriptions (from pharmacy fills) to diagnoses (from medical claims) involves two main steps: 1) assign opioid fills to claims based on timing and acuity, and 2) assign opioid refills to claims
 - i. Opioid/claim join using timing and acuity
 - 1. Create file of opioid fills from pharmacy fills data, using CDC file ["CDC opioid NDC_oral MME conversion_update_2020.xlsx"] to identify opioids
 - 2. Split opioid claims into two groups based on refill status: initial fills and refills (note this is using refill status indicated by the health fund. Many members have serial initial fills and not refills in these data; those would be in the initial fills file)
 - 3. Assign diagnosis category for each claim, using ICD-10 and procedure codes. Categories include “MSD surgery”, “Acute MSD injury”, “Chronic MSD”, and “Other diagnosis”
 - a. If more than one diagnosis category is present on a single claim, assign claim to the highest acuity (MSD Surgery, then Acute MSD Injury, then Chronic MSD, then Other diagnosis)
 - 4. Join claims with initial fills by member ID (UID)—this generates a many-to-many match
 - 5. Calculate time difference between claim date and fill date
 - a. If fill<before claim, use this information to generate opioid naïvety status for each claim
 - 6. If fill is 0-3 days after claim and the claim diagnosis category is not “Chronic MSD”, assign the opioid to the claim. If more than one claim fits the criteria, assign based on order other diagnoses, then MSD surgeries, lastly acute MSD injuries. If more than one claim is still eligible, use the smallest time difference between claim and fill to assign the fill
 - 7. Among the unlinked opioid fills, if fill is 0-30 days after a chronic MSD claim, assign opioid to that claim. If more than one claim meets the criteria, assign based on time difference (i.e., smallest time difference between claim and fill date)
 - ii. Assign opioid refills to claims

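### Section 9.4.2 applies independent-sample tests to two claims periods that share most or all of their members, so the planned p-values rest on the wrong variance

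*Combined protocol and SAP*

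**What the plan says.** For the primary claims endpoint, section 9.4.2 part a) instructs the analyst to "Run comparisons between baseline and follow-up time points". For the method it states "Comparisons involving two categorical variables will be made using Fisher"'s exact test, and then "Comparisons involving a continuous variable and a categorical variable will be made using Wilcoxon Rank Sum test or Kruskal Wallis test". Misuse, chronic use and opioid use disorder are all yes/no flags, so Fisher's test is the one that bears on them. The planned presentation is counts with percentages, or medians with quartiles. No standard error or interval for the change is specified.

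Section 9.4.1 sets the periods: 36 months of baseline (June 2019 to May 2022) and 12 months of follow-up (June 2022 to May 2023). It promises adjustment for period length and says nothing about members who appear in both.

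The population is described in three places:
- Section 9.3 takes the group eligible for benefits from May 2019 to May 2022.
- The data management appendix requires a "Health plan member (as opposed to dependent or retired) at some point during study period", gives the baseline dates for that period, and then says "Limit all analysis data (claims, fills) to members in the eligible/valids list".
- Sections 5 and 5.1 describe eligibility through May 2023.

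On linkage, section 9.4.8 says "Administrative claims data will be combined using a unique linking variable", but has the data analysed at group level by time point. On inference, section 9.1 says "There is no formal hypothesis testing in this trial".

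**The concern.** Fisher's exact, rank-sum and Kruskal-Wallis tests all assume that the people in one group are not the people in the other. Here the groups are two calendar periods in the same health funds. A member flagged in both periods enters the calculation as two unrelated people. No paired test, clustered model or cluster-robust variance is named anywhere in the documents. The sentence in 9.4.2 that calls all endpoints independent outcomes concerns endpoints, not members.

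Two things are at stake. The p-values attached to the primary claims change will not mean what they appear to mean. In addition, the study's stated product is input to the power calculation for a future trial (sections 9.1 and 9.2). An analysis that ignores pairing never estimates the within-member correlation, which that calculation would need if the future trial follows members over time.

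**Working it through.** **Inputs from the documents.** Section 9.2 expects 10,200 members in each of three funds: 3 × 10,200 = 30,600, which reproduces its total. The synopsis gives 33,300, but the main ratio below does not depend on N. No outcome rate, within-member correlation, overlap or alpha is stated.

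**Assumptions.** Correlation ρ of 0.2, 0.4 and 0.6 unless noted; overlap of 100% and 60%; outcome rate near 2% where one is needed; two-sided 5% level.

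**Variance of the change.** With m members seen in both periods,

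Var(p₂ − p₁) = p₁q₁/n₁ + p₂q₂/n₂ − 2ρ√(p₁q₁p₂q₂) · m/(n₁n₂).

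The independent-sample analysis drops the last term. With equal group sizes and rates, the unpaired SE divided by the SE allowing for pairing is 1/√(1 − ρ × overlap).

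| ρ | Full overlap | 60% overlap |
|---|---|---|
| 0.2 | 1/√0.80 = 1.12 | 1/√0.88 = 1.07 |
| 0.4 | 1/√0.60 = 1.29 | 1/√0.76 = 1.15 |
| 0.6 | 1/√0.40 = 1.58 | 1/√0.64 = 1.25 |

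**Direction.** By normal approximation, a nominal 5% test with no true change rejects 2.8%, 1.1% and 0.2% of the time at full overlap, and 3.7%, 2.5% and 1.4% at 60% overlap. Simulation agrees on direction (4,000 datasets per setting, 10,200 members, rate 2%, full overlap, equal-length periods). At ρ = 0, 0.3, 0.5 and 0.7, Fisher's test rejected in 4.2%, 1.7%, 0.2% and 0.03% of datasets, and exact McNemar in 4.2%, 4.3%, 4.0% and 3.7%.

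**Example.** Take 30,600 members in both periods, with a rate falling from 2.0% (612) to 1.8% (551). Fisher's p is 0.076. The joint probability is p₁₁ = p₁p₂ + ρ√(p₁q₁p₂q₂). Discordant counts are then 487/426, 373/312 and 259/198 at ρ = 0.2, 0.4 and 0.6, and exact McNemar p is 0.047, 0.022 and 0.005.

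**Why pairing alone is not the repair.** The figures above set period length aside. Outcomes counted as ever occurring over 36 months exceed those over 12 months even when nothing changes, and neither Fisher nor McNemar adjusts for that. Assume a 1% annual rate with no true change. At year-to-year correlations of 0.3, 0.5 and 0.7, the three-year rate is about 2.2%, 1.8% and 1.5%. For 10,200 members, comparing these with 1.0% gives:
- unpaired z = 0.012/0.00176 = 6.8, 0.008/0.00164 = 4.9 and 0.005/0.00156 = 3.2;
- paired z, using the same correlations between periods, = 0.012/0.00149 = 8.1, 0.008/0.00119 = 6.7 and 0.005/0.00087 = 5.7.

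A McNemar test on the unequal windows would make a spurious decline look firmer.

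**The case against.** The strongest reply is that this is a feasibility study. Section 3 says it is not powered to detect change and defines success as recruiting three funds and collecting the measures. No alpha or decision rule hangs on these tests. That stands, and it limits the weight of the point.

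Several stronger readings are tempting but go beyond the documents:

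- **That reported error bars are wrong.** The plan specifies none. The fault lies in the tests, and would carry over to an interval only if it were built the same way.
- **That the two periods contain exactly the same people.** The appendix and 9.3 point that way, but sections 5 and 5.1 do not, and 9.3 censors members who lose eligibility. The appendix also cites a sample-description file dated February 2023, before follow-up ended, so it may describe only the baseline extract. Substantial overlap is still likely under either definition, and any overlap with correlated outcomes breaks independence.
- **That the tests will produce false claims of benefit.** Ignoring positive pairing does the reverse. Variation between funds over time (three funds, an intervention delivered to funds) is also ignored and may push the other way, so the net direction is not settled.
- **That known pairing is being thrown away.** The variable list describes an identifier linking pharmacy and medical claims. Nothing says it stays the same between the two deliveries.
- **That a wrong variance will enter the future power calculation.** The documents say the data will inform it, not which variance will be used.

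**Conclusion.** The point holds as a mismatch between test and data. Section 9.4.2 treats two periods with substantial shared membership as independent samples, and nothing elsewhere in the plan corrects it. Under the assumed correlations of 0.2 to 0.6, the standard error behind those tests is 1.12 to 1.58 times too large at full overlap and 1.07 to 1.25 times at 60%. The correlations and overlaps are illustrative, and the ratios cover pairing only, not fund-level variation or unequal period length. Separately, 9.1 and 9.4.2 contradict each other on whether testing takes place, and the population definitions disagree. This should be fixed, but it does not threaten the study's feasibility conclusions. The worker surveys are outside the point: 9.4.2 names no test for them and their responses cannot be linked.

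**What to change.** In section 9.4.2, part a) item c, replace the independent-sample tests with the estimated change and its 95% confidence interval, from an analysis that clusters on the member ID and accounts for person-time. Either of these would serve:
- a GEE on member-years with an eligibility-time offset, which keeps members seen in only one period; or
- a McNemar-type paired difference on equal 12-month windows among members eligible in both.

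Report the result by fund and pooled, so that differences between funds are visible. Report the within-member correlation for planning the future trial. Drop the p-values or label them descriptive, so that 9.4.2 agrees with 9.1. Reconcile section 9.3 and the appendix with sections 5 and 5.1 on who is in the claims population for each period. Confirm with each fund that the same member ID is used in both deliveries.

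The cost is revised SAP wording and a little more analysis. No new variables are needed, but a fund that changed its IDs would have to supply a crosswalk or a consistent extract. The McNemar version omits members seen in only one period.
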